4.3.2 Safety Set

The Safety Set is defined as all subjects in the Enrolled Set who have safety follow-up data (including absence of AEs) in this long-term outcome study.

5. STUDY SUBJECTS

5.1 Disposition of Subjects

This section describes subject disposition for both the analysis sets and the study status.

The number of subjects included in each defined analysis set will be summarized by the antecedent treatment group as administered in Study OHB-607-202 (Standard Neonatal Care, SHP607 250 µg/kg/24 hours, and SHP607 400 µg/kg/24 hours) and overall.

Percentages will be provided using the Enrolled Set as the denominator.

The number and percentage of subjects who completed through the study visits (12-month, 18-month, 24-month, 30-month, 3-year, 3.5-year, 4-year, and 4.5-year CA), who completed the study, and who prematurely discontinued from the study will be presented for each treatment group and overall for the Enrolled Set. Primary reasons for premature discontinuation as recorded on the Study Completion page of the electronic case report

form (eCRF) will be summarized (number and percentage) by treatment group and overall. All subjects who prematurely discontinued will be listed for the Enrolled Set.

A by-subject listing of study completion information, including the reason for premature study discontinuation, where applicable, will be presented.

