- Health status (eg, health utility) will be measured by the Health Utilities Index Mark 2 (HUI2) and Mark 3 (HUI3).
- Health care resource use associated with inpatient visits, outpatient visits, emergency room visits, and visits to specialists will be assessed.

Secondary Safety Endpoints:

The secondary safety analysis will be based on:

- Targeted medical events occurring during the period of Study SHP607-203.
- Fatal SAEs.

Exploratory Endpoints:

- Caregiver Impact Questionnaire (CIQ): Descriptive statistics of the CIQ item responses at baseline, 24 months CA, and 5 years CA.
- EuroQol 5-dimensional 5-level descriptive system (EQ-5D-5L): Mean overall score on the EQ-5D-5L at 24 months CA, 3 years CA, 4 years CA, and change from 24 months CA.
- BabyScreen interactive electronic tablet application: Participation in the BabyScreen substudy is optional and has no impact on participation in the main study. The tool, used by children at 24 months CA to evaluate cognitive impairment, will be used for validation purposes only.
- Spirometry: Participation in the spirometry substudy is optional and has no impact on participation in the main study. Standard measures will be collected, including forced expiratory volume over 1 second (FEV1) and forced vital capacity (FVC).
- Cerebral MRI: Participation in the cerebral MRI substudy is optional and has no impact on participation in the main study. Brain volume and neuroanatomic abnormalities will be assessed utilizing cerebral MRI at specific sites with MRI capabilities.

Statistical Analyses:

Continuous variables will be summarized using descriptive statistics including the number of subjects, mean, standard deviation (SD), median, minimum, and maximum values.

Categorical variables will be summarized using frequencies and percentages.

As referred to in descriptions of summary statistics, treatment groups refer to the antecedent SHP607 dose groups (SHP607 at 250 µg/kg/day and SHP607 at 400 µg/kg/day), combined SHP607 dose groups, and standard neonatal care group.

For analysis purposes, baseline is defined as the first assessment in this study (Study SHP607-203).

Interim Analysis:

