9.7 General Statistical Methodology

For variables following a continuous distribution, tabular summaries will consist of number of subjects, mean, standard deviation, minimum, maximum, and median. For categorical variables, tabular summaries will include the frequency and the percentage in each category by treatment group. For analysis purposes, baseline is defined as the first assessment in this study (Study SHP607-203). Treatment groups refer to the antecedent SHP607 dose groups (SHP607 at 250 µg/kg/day and SHP607 at 400 µg/kg/day), combined SHP607 dose groups, and standard neonatal care group.

All efficacy analyses will be performed using the Enrolled Population.

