9.8 Safety Analyses

Safety data will be analyzed for the Safety Population.

For safety analyses, baseline is defined as the first assessment in this study (Study SHP607-203). Treatment groups refer to the antecedent SHP607 dose groups (SHP607 at 250 µg/kg/day and SHP607 at 400 µg/kg/day), combined SHP607 dose groups, and standard neonatal care group.

The primary safety analysis will be based on:

- AEs reported during the study period of SHP607-203

The secondary safety analysis will be based on:

- Targeted medical events occurring during the period of Study SHP607-203.
- Fatal SAEs

Adverse events will be coded using the Medical Dictionary for Regulatory Activities. The number of events, incidence, and percentage of AEs will be calculated overall, by system organ class (SOC), by preferred term, and by treatment group. Adverse events will be further summarized by severity and relationship to prior investigational product. Adverse events related to investigational product, AEs leading to withdrawal, SAEs, and deaths will be similarly summarized/listed.

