2. OBJECTIVES

2.1 Primary Objectives

The primary objectives of the study are:

- To evaluate long-term efficacy outcomes following previously administered short-term exposure to SHP607, as compared to a standard neonatal care group, as assessed by chronic respiratory morbidity (CRM) outcomes.
- To evaluate the long-term safety outcomes following previously administered short-term exposure to SHP607, as compared to a standard neonatal care group.

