7. SAFETY ANALYSIS

The safety analysis will be performed using the Safety Set. All safety analyses will be conducted according to the treatment the subject actually received in Study OHB-607-202.

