7.1 Adverse Events

Adverse events will be coded using Medical Dictionary for Regulatory Activities (MedDRA) Version 24.0 or newer. For the purposes of this study only the following adverse events will be presented:

- Specified targeted medical events (Protocol Section 8.1.4)
- AEs related to investigational product (as administered in Study OHB-607-202)
- AEs leading to withdrawal from the study
- Serious AEs that occur during the study period or were previously present and worsen during the study period.

If it is determined that any of the following targeted medical events have been experienced by a subject, they will be recorded as AEs or SAEs, as appropriate, regardless of relationship to prior investigational product (as administered in Study OHB-607-202). The targeted medical events are considered as AEs of important potential risks and identified based on a list of pre-specified preferred terms (PTs):

- Intracranial hypertension: intracranial pressure increased, benign intracranial hypertension, fontanelle bulging, delayed fontanelle closure
- Any abnormality of glucose metabolism: hypoglycaemia, hypoglycaemia neonatal, blood glucose decreased
- Tonsillar hypertrophy (based on tonsil examination [part of the physical examination]): tonsillar hypertrophy, adenoidal hypertrophy, thymus enlargement, hypoacusis, snoring, ear tube insertion, tonsillectomy, adenoidectomy, sleep apnoea syndrome
- Increased cardiac size: cardiomegaly, cardiac hypertrophy, cardiac septal hypertrophy, ventricular hypertrophy, atrial hypertrophy, left ventricular hypertrophy, right ventricular hypertrophy, left atrial hypertrophy, right atrial hypertrophy, cardiomyopathy, cardiomyopathy neonatal, hypertrophic cardiomyopathy

An overall summary of the number of subjects as well as the number of events in each treatment group and overall will be presented, including the number and percentage of subjects with:

- Any AE (as specified in Protocol Section 8.1)
- Any SAE
- Any severe AE
- Any AE related to investigational product (IP) as administered in Study OHB-607-202

- Any SAE related to IP as administered in Study OHB-607-202
- Any severe AE related to IP as administered in Study OHB-607-202
- Any AE related to procedures performed in this study (SHP607-203)
- Any SAE related to procedures performed in this study (SHP607-203)
- Any severe AE related to procedures performed in this study (SHP607-203)
- Any AE leading to study discontinuation
- Any SAE leading to death

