The number and percentage of subjects reporting AEs, as well as the number of events (except for tables by the maximum severity), in each treatment group and overall will be tabulated, respectively, in following ways:

- By system organ class (SOC) and PT for all AEs
- By the maximum severity, SOC and PT for all AEs
- By SOC and PT for all AEs considered related to IP as administered in Study OHB-607-202
- By SOC and PT for all AEs considered related to study procedures
- By SOC and PT for all AEs leading to death
- By SOC and PT for all AEs leading to study discontinuation
- By SOC and PT for all SAEs
- By risk term, seriousness, and relationship to antecedent IP for AEs of important potential risks
- Most frequent AEs by PT (sorted by frequency, occurring in $\geq 5\%$ of subjects in any treatment arm)

In tables by severity or relationship, missing severity or missing relationship imputation will be applied, and handling of those missing cases are detailed in Section [9.2.2](#) and [9.2.3](#), respectively. If a subject had multiple occurrences of the same AEs, the subject will be counted only once per SOC and once per PT at the maximum severity. Handling of incomplete AE start/end dates is described in Section [9.2.1](#).

All AEs will be presented in a data listing. Separate data listings will be presented for AEs related to the antecedent IP, AEs related to study procedures, AEs leading to death, SAEs and AEs of important potential risks.

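### Does the SAP need to name the combined SHP607 group that the protocol lists for its safety tables?

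*SAP*

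**What the plan says.** **Protocol.** Section 9.7 begins its definition "Treatment groups refer to the antecedent SHP607 dose groups", names the 250 and 400 µg/kg/day groups, and continues with the combined doses and standard care. Section 9.8 repeats this for safety, ending "combined SHP607 dose groups, and standard neonatal care group". The synopsis has the same definition ("As referred to in descriptions of summary statistics, treatment groups refer to the antecedent SHP607 dose groups").

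**SAP.** Groups are spelled out once, in Section 5.1, where the number of subjects in each analysis set "will be summarized by the antecedent treatment group as administered in Study OHB-607-202 (Standard Neonatal Care, SHP607 250", followed by the 400 dose and an overall total. Section 5.2 (baseline) and Section 7.1 (adverse events) refer to treatment group and overall without listing the groups again. Section 7 adds "All safety analyses will be conducted according to the treatment the subject actually received in Study OHB-607-202". Section 9.1 ties the overall denominator to all subjects in the analysis set, so it includes the standard-care children.

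Section 10 declares one departure from the protocol, the dropped efficacy endpoints. Section 1 states that the SAP elaborates the designated safety analyses of protocol amendment 1 and that table, figure and listing specifications are held elsewhere.

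**The concern.** Safety is the only analysis left after early termination, and its objective is "To evaluate the long-term safety outcomes following previously administered short-term exposure to SHP607, as compared to a standard neonatal care group". That objective contrasts exposure with no exposure, so the combined SHP607 group is its natural left-hand side. The protocol names that group for safety and the SAP does not. The loss of the efficacy analyses does not explain the gap.

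The overall column cannot stand in for it, because it mixes exposed and unexposed children. This shows most clearly in rows such as "Any AE related to investigational product (IP) as administered in Study OHB-607-202" and in the table "By SOC and PT for all AEs considered related to IP as administered in Study OHB-607-202". The only total the SAP names for these has a denominator that includes children who never received the product. If a protocol-defined group had been removed without a declaration and information had gone with it, a correction would be due.

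**Working it through.** There is no stated figure to reproduce: no sample size was calculated, and the safety analyses carry no test or interval. The check has two parts: whether the text shows a change, and what would be lost if the column were absent.

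**1. Is it a change?** The list in SAP 5.1 sits in the disposition sentence about analysis-set counts. The adverse event section has no list. A document that elaborates the protocol's safety analyses, and uses the protocol's term *treatment group* without redefining it there, can be read as keeping the 9.8 definition. The separate table specifications were not available and may already contain the column. The text therefore supports *not restated*; it does not establish *removed*.

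**2. How many children?** SAP 3.1 says enrolment was below 10% of plan.
- 0.10 × 477 = 47.7, so at most 47.
- If plan means the 382 expected completers, 0.10 × 382 = 38.2, so at most 38.

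Arm sizes are not given. An even split is assumed: about 31 exposed and 16 control (of 47), or 25 and 13 (of 38).

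**3. Adverse event tables.** Each child is analysed under one treatment received, so the dose columns share no children. With x subjects affected out of n:

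combined percentage = (x₂₅₀ + x₄₀₀) / (n₂₅₀ + n₄₀₀)

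Event counts add in the same way. Under SAP 9.1 the denominators are the group totals, so every input is in the tables and nothing is lost. The table of frequent events (at least 5% in any arm) is also unaffected. The combined percentage is a weighted average of the two dose percentages and cannot exceed the larger, so a combined column could never bring in a term that the dose arms had not.

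**4. Product-related rows.** These are 3 of the 11 overview rows and 2 of the 9 tabulations in SAP 7.1. If no control event counts as related:

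overall percentage = combined percentage × (exposed children / all children)

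- Even split: 31/47 = 0.66, or 25/38 = 0.66.
- Exposed share of 50% to 80% (assumed range): factor 0.5 to 0.8.
- A 10% combined rate would show as 6.7% overall at two thirds exposed.

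The identity ignores any control event with a missing relationship, which SAP 9.2.3 would impute as related. The percentage in each dose column is unaffected.

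**5. Baseline.** Two continuous variables (corrected age at enrolment and gestational age at birth) with eight statistics each (SAP 9.1) give 16. From the arm columns, n, mean, SD, minimum and maximum can be combined (mean and SD up to rounding). Median, Q1 and Q3 cannot: 2 × 3 = 6 of 16. Protocol 9.7 asks for the median but not the quartiles, so only 2 of the 6 are protocol-type summaries. SAP 5.2 promises a listing of all baseline characteristics for every child, so all six can be computed from about 31 listed values at the assumed split.

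**The case for a change.** The best case for a change is this. Protocol 9.3 makes the SAP the place for methods and definitions, and SAP 5.1 gives an explicit list that differs from the protocol's. A programmer could reasonably take that list as the column set for every table. If the separate specifications do the same, a protocol-defined safety group disappears with no entry in Section 10. The cost of repair is one sentence and one column, and readers should not have to add columns to see the contrast that the objective names.

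The textual part stands. The combined group is not in the SAP, the overall column includes controls, and Section 10 is silent. Harm does not follow. Protocol 9.8 plans only counts, incidence and percentages for safety, with no between-group difference or interval. The one explicit combined-dose contrast is in Protocol 9.7.1, for efficacy, and SAP Sections 6 and 10 state that efficacy will not be analysed. A reader of the product-related rows sees both dose columns and the standard-care column beside the total, so the diluted overall figure is unlikely to mislead.

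**Conclusion.** The mismatch in wording is real, but it calls for no change. At most it is a definition left unrepeated in an abbreviated, descriptive plan for a terminated study of at most 47 children. Analysts can fill it from Protocol 9.8 or by adding two columns.

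No adverse event information is lost. Six baseline statistics need the listing that the SAP already provides. The overall percentage for product-related events understates the combined one by a known factor, about 0.66 at an even split and 0.5 to 0.8 over the assumed range, while the dose-specific percentages remain right.

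These factors rest on assumed arm sizes and on no control event being imputed as related. The conclusion does not depend on them, because the additivity in step 3 holds for any split. Whether the final tables carry a combined column cannot be settled from the two documents, but the safety conclusions would be the same either way.

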5.2 Demographic and Other Baseline Characteristics

Descriptive summaries of demographic and baseline characteristics will be presented by treatment group and overall for the Enrolled Set. The following demographic and baseline characteristics will be summarized: CA (months) at enrollment, gestational age (GA) at birth (weeks), sex, ethnicity, and race. A listing will be presented to show all the demographic and baseline characteristics for each subject in the Enrolled Set.

5.3 Exposure to Investigational Product

Exposure to investigational product is not applicable as no investigational product is administered in this study.

6. EFFICACY ANALYSES

No efficacy data will be analyzed nor listed for this study due to early termination and lack of assessments.

7. SAFETY ANALYSIS

The safety analysis will be performed using the Safety Set. All safety analyses will be conducted according to the treatment the subject actually received in Study OHB-607-202.

7.1 Adverse Events

Adverse events will be coded using Medical Dictionary for Regulatory Activities (MedDRA) Version 24.0 or newer. For the purposes of this study only the following adverse events will be presented:

- Specified targeted medical events (Protocol Section 8.1.4)
- AEs related to investigational product (as administered in Study OHB-607-202)
- AEs leading to withdrawal from the study
- Serious AEs that occur during the study period or were previously present and worsen during the study period.

If it is determined that any of the following targeted medical events have been experienced by a subject, they will be recorded as AEs or SAEs, as appropriate, regardless of relationship to prior investigational product (as administered in Study OHB-607-202). The targeted medical events are considered as AEs of important potential risks and identified based on a list of pre-specified preferred terms (PTs):

- Intracranial hypertension: intracranial pressure increased, benign intracranial hypertension, fontanelle bulging, delayed fontanelle closure
- Any abnormality of glucose metabolism: hypoglycaemia, hypoglycaemia neonatal, blood glucose decreased
- Tonsillar hypertrophy (based on tonsil examination [part of the physical examination]): tonsillar hypertrophy, adenoidal hypertrophy, thymus enlargement, hypoacusis, snoring, ear tube insertion, tonsillectomy, adenoidectomy, sleep apnoea syndrome
- Increased cardiac size: cardiomegaly, cardiac hypertrophy, cardiac septal hypertrophy, ventricular hypertrophy, atrial hypertrophy, left ventricular hypertrophy, right ventricular hypertrophy, left atrial hypertrophy, right atrial hypertrophy, cardiomyopathy, cardiomyopathy neonatal, hypertrophic cardiomyopathy

An overall summary of the number of subjects as well as the number of events in each treatment group and overall will be presented, including the number and percentage of subjects with:

- Any AE (as specified in Protocol Section 8.1)
- Any SAE
- Any severe AE
- Any AE related to investigational product (IP) as administered in Study OHB-607-202

- Any SAE related to IP as administered in Study OHB-607-202
- Any severe AE related to IP as administered in Study OHB-607-202
- Any AE related to procedures performed in this study (SHP607-203)
- Any SAE related to procedures performed in this study (SHP607-203)
- Any severe AE related to procedures performed in this study (SHP607-203)
- Any AE leading to study discontinuation
- Any SAE leading to death

The number and percentage of subjects reporting AEs, as well as the number of events (except for tables by the maximum severity), in each treatment group and overall will be tabulated, respectively, in following ways:

- By system organ class (SOC) and PT for all AEs
- By the maximum severity, SOC and PT for all AEs
- By SOC and PT for all AEs considered related to IP as administered in Study OHB-607-202
- By SOC and PT for all AEs considered related to study procedures
- By SOC and PT for all AEs leading to death
- By SOC and PT for all AEs leading to study discontinuation
- By SOC and PT for all SAEs
- By risk term, seriousness, and relationship to antecedent IP for AEs of important potential risks
- Most frequent AEs by PT (sorted by frequency, occurring in $\geq 5\%$ of subjects in any treatment arm)

In tables by severity or relationship, missing severity or missing relationship imputation will be applied, and handling of those missing cases are detailed in Section [9.2.2](#) and [9.2.3](#), respectively. If a subject had multiple occurrences of the same AEs, the subject will be counted only once per SOC and once per PT at the maximum severity. Handling of incomplete AE start/end dates is described in Section [9.2.1](#).

All AEs will be presented in a data listing. Separate data listings will be presented for AEs related to the antecedent IP, AEs related to study procedures, AEs leading to death, SAEs and AEs of important potential risks.

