8.1.4 Targeted Medical Events

If it is determined that any of the following targeted medical events have been experienced by a subject, they will be recorded as AEs or SAEs (refer to Section 8.2.3), as appropriate, regardless of relationship to prior investigational product (SHP607 as administered in Study SHP607-202):

- Intracranial hypertension
- Any abnormality of glucose metabolism (eg, hypoglycemia, hyperglycemia, and diabetes)
- Tonsillar hypertrophy (based on tonsil examination [part of the physical examination])
- Increased cardiac size

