3.2.4 Safety Endpoints

The safety endpoints of this study are:

- Adverse events (AEs) reported during the study period of SHP607-203.
- Targeted medical events occurring during the period of Study SHP607-203.
- Fatal serious adverse events (SAEs)

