10. CHANGES TO ANALYSIS SPECIFIED IN PROTOCOL

Protocol planned efficacy endpoints are not listed or analyzed in this abbreviated SAP due to early termination of the study.

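### The SAP counts the glucose targeted medical event from low-glucose terms only, so hyperglycemia and diabetes, both named in the protocol, are left out of the risk-term table without being declared

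*SAP*

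**What the plan says.** Protocol 8.1.4 lists four targeted medical events, to be recorded as AEs or SAEs whatever their relationship to the earlier treatment. The glucose item reads "Any abnormality of glucose metabolism (eg, hypoglycemia, hyperglycemia, and diabetes"). Protocol 9.8 makes targeted medical events, together with fatal SAEs, the secondary safety analysis. SAP 3.2.4 keeps them as a safety endpoint: "Targeted medical events occurring during the period of Study SHP607-203".

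SAP 7.1 opens by naming the adverse events to be presented, the first being "Specified targeted medical events (Protocol Section 8.1.4"). It then says that targeted events are treated as AEs of important potential risks and are "identified based on a list of pre-specified preferred terms (PTs"). For glucose the list is: "Any abnormality of glucose metabolism: hypoglycaemia, hypoglycaemia neonatal, blood glucose decreased".

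The events so identified feed one table, "By risk term, seriousness, and relationship to antecedent IP for AEs of important potential risks", and one separate listing. The only change from the protocol that SAP Section 10 declares is: "Protocol planned efficacy endpoints are not listed or analyzed in this abbreviated SAP due to early termination of the study".

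**The concern.** The protocol's definition covers both directions of glucose disturbance. The SAP keeps the wide label but counts one direction. A child with diabetes or hyperglycemia would be recorded as having a targeted medical event, as Protocol 8.1.4 requires, and would then be missing from the only table that shows targeted events as a group.

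This matters more than it would in a full report. SAP Section 6 drops all efficacy analysis, so adverse events, targeted medical events and fatal SAEs are the only endpoints still analysed. A reader who goes to the targeted-event table for the glucose result would see a count that excludes two of the three conditions the protocol names, under a heading that claims to include them. That row could read zero while the all-AE table in the same report shows diabetes.

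**Working it through.** The SAP states no figure to reproduce. The check is a match of definitions, a trace of the outputs affected, and simple arithmetic on size.

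**1. Match the protocol's named conditions to the SAP's preferred terms.**

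| Named in Protocol 8.1.4 | Matching terms in SAP 7.1 |
|---|---|
| Hypoglycemia | 3 of 3 (hypoglycaemia; hypoglycaemia neonatal; blood glucose decreased) |
| Hyperglycemia | 0 of 3 |
| Diabetes | 0 of 3 |

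The list carries no wording such as *for example* or *including*, so as written it is closed. Two of the three named conditions contribute zero.

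**2. Is the narrowing evidently deliberate?** Nothing in the documents says so.
- Section 10 mentions only efficacy endpoints, and the row label was not changed.
- The tonsillar list has 9 terms and the cardiac list 12, both wider than their labels. Only the glucose list omits conditions that Protocol 8.1.4 names.
- Protocol 1.1.4 describes glycemic instability in these infants as including both low and high glucose.
- One of the three glucose terms is a neonatal term, although follow-up starts at 12 months corrected age.

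**3. Trace the outputs in SAP 7.1.**
- The overall AE summary has no row for targeted events.
- Of the nine tabulations that follow it, one (by risk term) depends on the term list.
- There are six listings: all AEs, plus five separate ones (related to the antecedent product, related to study procedures, leading to death, SAEs, important potential risks). One of the six depends on the term list.
- A hyperglycemia or diabetes event would still appear in the all-AE tables by SOC and preferred term and by maximum severity, and in the full listing ("All AEs will be presented in a data listing"). It would also appear in the SAE and product-related outputs where it qualifies.

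**4. Size of one omission.** SAP 3.1 puts enrolment below 10% of the planned number, about 477.
- Ceiling: 0.10 × 477 = 47.7, so at most 47 children.
- Even split over three arms (assumed, since arm sizes are not given): 47 / 3 = 15.7, about 16.
- One child in an arm of 16: 1/16 = 6.25%, about 6 percentage points.
- Illustrative range: 1/12 = 8.3 points to 1/20 = 5.0 points.
- Overall column at the ceiling: 1/47 = 2.1%.

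**5. Visibility elsewhere.** The most-frequent-AE table takes preferred terms that reach 5% in any arm. One child reaches that level when 1/n ≥ 0.05, that is, n ≤ 20. In any arm of 20 or fewer, a single case of diabetes would enter that table while adding nothing to the glucose risk row.

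**The case against.** The strongest reply is that nothing is lost. Every such event remains in the all-AE outputs, and with at most 47 children a reader can find it in the listing. The report is descriptive, no inference uses the row, and the protocol prescribes no risk-term table. This stands as a limit on the consequence: the fault is a wrong grouped count in one table and one listing, not a suppressed event. It does not make the row correct, because targeted events are a named endpoint and this is the table that summarises them.

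Second, the harm depends on an event occurring. The visit procedures in Protocol 7.1 list no glucose or other laboratory test, so cases would come to light through caregiver report or outside records, and there may be none. That is true. If there are none, the row is right under either list. But a counting rule should not depend on the event being absent.

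Third, SAP Section 1 places table and listing specifications in a separate document, which was not available for this review and might hold a wider list. SAP 7.1 does not point to one. If it exists, the two documents disagree and the SAP text still needs correcting.

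Fourth, the percentage-point figures rest on a ceiling for the Enrolled Set and an assumed split, whereas the safety tables use the Safety Set, which may be smaller or uneven. They are illustrative only.

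**Conclusion.** The concern holds. SAP 7.1 contradicts both Protocol 8.1.4 and its own cross-reference to that section, and the change is not declared. If any hyperglycemia or diabetes event has been recorded, the targeted-event count for glucose would be too low by every such event. The effect is confined to the risk-term table and the listing of important potential risks. One omitted child would be worth about 6 percentage points in an arm of 16, on the assumption of full enrolment to the ceiling and an even split. This should be fixed before reporting. It does not threaten the study's overall safety record, because the events remain in the all-AE outputs. The conclusion that two of three conditions are unmatched rests on the SAP text alone and needs no assumption about numbers.

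**What to change.** Before the tables are run, extend the glucose list in SAP 7.1 with terms for high glucose (hyperglycaemia, blood glucose increased) and for diabetes mellitus, so that it covers what Protocol 8.1.4 names. Check that the separate table and listing specifications carry the same list. Showing low-glucose and high-glucose or diabetes events on separate lines under the common heading would help the reader but is optional.

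If the sponsor does intend a hypoglycemia-only risk term, rename the row accordingly, declare and justify the narrowing in SAP Section 10, and still report the full glucose count as the protocol defines it.

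The cost is a few lines of SAP text and a revised term lookup. No new data collection is needed.
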